## **7. PLANNED ANALYSIS**

The format of the listings and tables will follow the BI guideline "Reporting of clinical trials and project summaries" (6).

The individual values of all subjects will be listed. Listings will be sorted by treatment group, subject number and visit (if visit is applicable in the respective listing). AE listings will be sorted by assigned treatment group (see [Section 7.8.1](#) below for details). The listings will be contained in Appendix 16.2 (SDL) of the CTR.

The following standard descriptive statistical parameters will be displayed in summary tables of continuous variables:

N	number of non-missing observations
Mean	arithmetic mean
SD	standard deviation
Min	minimum
Median	median
Max	maximum

For plasma and urine concentrations as well as for all PK parameters the following descriptive statistics will additionally be calculated:

CV	arithmetic coefficient of variation
gMean	geometric mean
gCV	geometric coefficient of variation

For PK parameters the following descriptive statistics will additionally be calculated:

P10	10th percentile
Q1	1st quartile
Q3	3rd quartile
P90	90th percentile

The data format for descriptive statistics of plasma and urine concentrations will be identical with the data format of the respective concentrations. The descriptive statistics of PK parameters will be calculated using the individual values with the number of decimal places as provided by the evaluation program. Then the individual values as well as the descriptive statistics will be reported with three significant digits in the CTR.

Tabulations of frequencies for categorical data will include all possible categories and will display the number of observations in a category as well as the percentage (%) relative to the respective treatment group. Percentages will be rounded to integer numbers. The category missing will be displayed only if there are actually missing values. Percentages will be based on all subjects in the respective subject set whether they have non-missing values or not.

## **7.1 DEMOGRAPHIC AND OTHER BASELINE CHARACTERISTICS**

Only descriptive statistics are planned for this section of the CTR. These will be based on the TS.

## **7.2 CONCOMITANT DISEASES AND MEDICATION**

Concomitant diseases and non-drug therapies will be coded according to the most recent version of MedDRA. Concomitant medications and drug therapies will be coded according to the most recent version of the World Health Organisation – Drug Dictionary (WHO-DD). The coding version number will be displayed as a footnote in the respective output.

Only descriptive statistics are planned for this section of the CTR. These will be based on the TS.

**CTP Section 7.2.5:** *Previous and concomitant therapies will be presented per treatment group without consideration of time intervals and treatment periods.*

A drug or non-drug therapy will be considered concomitant to a treatment, if it

- is ongoing at the time of study drug administration, or
- starts within the analysis phase of the respective treatment (see [Section 6.1](#) for a definition of treatments and analysis phases).

The diagnoses and drug as well as non-drug therapies will be listed. Subjects without any concomitant disease or concomitant therapy will be marked with a “No” in the respective column.

The relevance of the concomitant therapies to the evaluation of PK will be decided no later than at the RPM.

## **7.3 TREATMENT COMPLIANCE**

Treatment compliance will not be analysed as a specific endpoint. Any deviations from complete intake will be addressed in the Report Planning Meeting (cf. [Section 6.2](#)) and described in the CTR.

**CTP Section 4.3:** *“Compliance will be assured by administration of all trial medication in the trial centre under supervision of the investigating physician or a designee. The measured plasma concentrations and/or urinary excretion of trial medication will provide additional confirmation of compliance.”*

## **7.4 PRIMARY OBJECTIVE ANALYSIS**

### **7.4.1 Main analysis**

The primary and secondary endpoints will be analysed descriptively, as described in the **CTP Section 7.2.2** and **Section 7.2.3**.

**CTP Section 7.2.2:** “*To avoid underestimation of the total recovery of [ $^{14}\text{C}$ ], the excretion during the non-sampling phase of the study will be estimated using linear interpolation between the observed 24-h sampling periods before and after the non-sampling period for urine and faeces respectively.*”

The analysis of primary and secondary endpoints will be based on the PKS. Subjects in the PKS may not contribute data to every statistical analysis of PK endpoints, in case specific PK endpoints of this subject are missing or excluded for the following reasons.

#### Exclusion of PK parameters

The ADS ADPP contains column variables APEX and APEXCO indicating inclusion/exclusion (APEX) of a PK parameter and an analysis flag comment (APEXCO). All analyses based on the PKS are based on PK parameter values which are not flagged for exclusion, i.e. with APEX equal to "Included".

**CTP Section 7.2.1.2:** “*Plasma, urine, faeces, and vomit (as applicable) concentration data and parameters of a subject will be included in the statistical PK analyses if they are not flagged for exclusion due to a protocol deviation relevant to the evaluation of PK (to be decided no later than in the Report Planning Meeting) or due to PK non-evaluability (as revealed during data analysis, based on the criteria specified below). Exclusion of a subject's data will be documented in the CTR.*”

#### Exclusion of PK concentrations

The ADS ADPC (PK concentrations per time-point or per time-interval) contains column variables ACEX or ACEXCO indicating inclusion/exclusion (ACEX) of a concentration and an analysis flag comment (ACEXCO). Exclusion of a concentration depends on the analysis flag comment ACEXCO. For example, if ACEXCO is set to "ALL CALC", the value will be excluded for all types of analyses based on concentrations. If ACEXCO is set to "DESC STATS" the value will be excluded from descriptive evaluations per planned time point/time interval. If ACEXCO contains the addition "TIME VIOLATION" or "TIME DEVIATION", the value can be used for further analyses based on actual times. If ACEXCO is set to "HALF LIFE", the value will be excluded from half-life calculation only; the value is included for all other analyses. Excluded concentration itself will be listed in the CTR associated with an appropriate flag.

Further details are given in “Noncompartmental Pharmacokinetic / Pharmacodynamic Analyses of Clinical Studies” (4) and “Description of Analytical Transfer Files and PK/PD Data Files” (5)

## **7.5 SECONDARY OBJECTIVE ANALYSIS**

### **7.5.1 Key secondary objective analysis**

This section is not applicable as no key secondary objective has been specified in the CTP.

### **7.5.2 Secondary objective analysis**

This section is not applicable as no secondary objective has been specified in the CTP.

## **7.6 FURTHER OBJECTIVE ANALYSIS**

### **7.6.2 Safety parameters**

Safety and tolerability will be analysed as described in [Section 7.8](#) of this TSAP.

## **7.7 EXTENT OF EXPOSURE**

Since only a single dose is administered per subject, a listing will be sufficient to give account of the extent of exposure.

## **7.8 SAFETY ANALYSIS**

All safety analyses will be performed on the TS.

### **7.8.1 Adverse Events**

AEs will be coded with the most recent version of MedDRA.

The analyses of AEs will be descriptive in nature. All analyses of AEs will be based on the number of subject with AEs and not on the number of AEs.

For further details on summarization of AE data, please refer to "Analysis and Presentation of Adverse Event Data from Clinical Trials" ([7](#)) and "Handling of missing and incomplete AE dates" ([3](#)).

The analysis of AEs will be based on the concept of treatment emergent AEs. That means that all AEs will be assigned to screening, on-treatment or follow-up phases as defined in [Section 6.1](#). AEs will be analysed based on actual treatments on the recorded time of AE onset, as defined in [Table 6.1: 1](#).

An overall summary of AEs will be presented. This summary will include summary statistics for the class of adverse events of special interest (AESIs).

**CTP Section 5.2.6.1.4:** “*The following are considered as AESIs:*

**Potential severe DILI**

*A potential severe Drug Induced Liver Injury (DILI) that requires follow-up is defined by the following alterations of hepatic laboratory parameters:*

- o An elevation of AST (aspartate aminotransferase) and/or ALT (alanine aminotransferase)  $\geq 3$ -fold ULN combined with an elevation of total bilirubin  $\geq 2$ -fold ULN measured in the same blood sample, or in samples drawn within 30 days of each other, or*
- o Aminotransferase (ALT, and/or AST) elevations  $\geq 10$ -fold ULN*

*These lab findings constitute a hepatic injury alert and the participants showing these lab abnormalities need to be followed up according to the ‘DILI checklist’ provided in the ISF. In case of clinical symptoms of hepatic injury (icterus, unexplained encephalopathy, unexplained coagulopathy, right upper quadrant abdominal pain, etc.) without lab results (ALT, AST, total bilirubin) available, the investigator should make sure that these parameters are analysed, if necessary in an unscheduled blood test. Should the results meet the criteria of hepatic injury alert, the procedures described in the DILI checklist should be followed.”*

The investigator had to classify on the eCRF whether an observed AE was an AESI or not. According to ICH E3 ([8](#)), in addition to Deaths, and serious adverse events, ‘other significant’ AEs need to be listed in the clinical trial report. These will be any non-serious adverse events that led to an action taken with study drug (e.g. discontinuation or dose reduced or interrupted).

The frequency of subjects with AEs will be summarised by treatment, primary SOC and preferred term. Separate tables will be provided for subjects with

- AEs, which were considered by the investigator to be drug related
- SAEs
- AESIs
- AEs summarized by worst intensity.

The SOCs and preferred terms within SOCs will be sorted by descending frequency over all treatment groups.

For disclosure of AE data on ClinicalTrials.gov, the frequency of subjects with non-serious AEs occurring with an incidence of greater than 5 % (in preferred terms) will be summarised

by treatment, primary SOC and preferred term. The frequency of subjects with SAEs will also be summarised.

For disclosure of AE data in the EudraCT register, the frequency of AEs, the frequency of non-serious AEs with an incidence of greater than 5 % (in preferred terms) and the frequency of SAEs will be summarized.

For support of lay summaries, the frequency of subjects with drug-related SAEs will be summarized by treatment, primary SOC and preferred term.

### **7.8.2      Laboratory data**

The analyses of laboratory data will be descriptive in nature and will be based on BI standards "Handling, Display and Analysis of Laboratory Data" (9).

Analyses will be based on normalised values, which means transforming to a standard unit and a standard reference range. The original values will be analysed if the transformation into standard unit is not possible for a parameter.

Descriptive statistics of laboratory values over time and for the difference from baseline (see [Section 6.7](#)) will be provided. Frequency tables of changes between baseline and last value on treatment with respect to the reference range will be presented.

Unscheduled measurements of laboratory data will be assumed to be repeat measurements of the most recent scheduled measurement (e.g. for follow-up or confirmation of a particular value). Therefore, unscheduled measurements will be assigned to the planned time point of the previous scheduled measurement. Descriptive statistics will be calculated by planned time point based on the worst value of the subject at that planned time point (or assigned to that planned time point).

Laboratory data will be compared to their reference ranges. Values outside the reference range will be highlighted in the listings. Possibly clinically significant laboratory values (according to standard BI criteria defining possibly clinically significant abnormalities) will be listed separately.

In general, clinically significant abnormal laboratory values are only those identified either in the Investigator's comments or at the Report Planning Meeting at the latest. With regard to laboratory abnormal values identified at the site it is the Investigator's responsibility to decide whether a lab value is clinically significantly abnormal or not. Those will be reported as baseline conditions (prior to first administration of study treatment) or as AEs (after first administration of study treatment).

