Enzymes	AST [Aspartate aminotransferase] /GOT, SGOT ALT [Alanine aminotransferase] /GPT, SGPT Alkaline Phosphatase Gamma-Glutamyl Transferase Creatine Kinase [CK] Creatine Kinase Isoenzyme MB [only if CK is elevated] Lactate dehydrogenase Lipase Amylase	X X X X X X X X	X X X X X X X X	-- -- -- -- -- -- -- --	X X X X X X X X
Hormones	Thyroid Stimulating Hormone	X	--	--	--

Proprietary confidential information © 2023 Boehringer Ingelheim International GmbH or one or more of its affiliated companies

Table 5.2.3: 1 Routine laboratory tests (cont.)

Functional lab group	BI test name [comment/abbreviation]	A	B	C	D
Substrates	Glucose (serum)	X	X	--	X
	Creatinine	X	X	--	X
	Bilirubin, Total	X	X	--	X
	Bilirubin, Direct	X	X	--	X
	Protein, Total	X	X	--	X
	C-Reactive Protein (Quant)	X	X	--	X
	Blood Urea Nitrogen	X	X	--	X
	Uric Acid	X	--	--	--
	Cholesterol, total	X	--	--	--
	Triglycerides	X	--	--	--
Electrolytes	Sodium	X	X	--	X
	Potassium	X	X	--	X
	Calcium	X	X	--	X
Urinalysis (Stix)	Urine Nitrite (qual)	X	--	--	X
	Urine Protein (qual)	X	--	--	X
	Urine Glucose (qual)	X	--	--	X
	Urine Ketone (qual)	X	--	--	X
	Urobilinogen (qual)	X	--	--	X
	Urine Bilirubin (qual)	X	--	--	X
	Urine RBC/Erythrocytes (qual)	X	--	--	X
	Urine WBC/Leucocytes (qual)	X	--	--	X
	Urine pH	X	--	--	X
Urine sediment (Urine sediment examinations will only be performed if there is an abnormality in urinalysis in accordance with Clinical Laboratory, standard procedure)	Only positive findings will be reported (for instance, the presence of sediment bacteria, casts in sediment, squamous epithelial cells, erythrocytes, leukocytes)				

A: parameters to be determined at Visit 1 (screening examination)

B: parameters to be determined at Visit 2 on Day -1, Day 2, and Day 15 (for time points refer to [Flow Chart](#))

C: parameters to be determined at Visit 2 on Day 1, Day 3, Day 4, Day 8, and Day 10 (for time points refer to [Flow Chart](#))

D: parameters to be determined at Visit 3 (end of study examination)

The tests listed in Table [5.2.3: 2](#) are exclusionary laboratory tests that may be repeated as required. The results will not be entered in the CRF/database and will not be reported in the CTR. Except for drug screening, it is planned to perform these tests during screening only. Drug screening will be performed at screening and on Day -1 of the treatment period.

Proprietary confidential information © 2023 Boehringer Ingelheim International GmbH or one or more of its affiliated companies

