5.2.6.1.4 Adverse events of special interest

The term adverse events of special interest (AESI) relates to any specific AE that has been identified at the project level as being of particular concern for prospective safety monitoring and safety assessment within this trial, e.g. the potential for AEs based on knowledge from other compounds in the same class. AESIs need to be reported to the sponsor’s Pharmacovigilance Department within the same timeframe that applies to SAEs, please see Section [5.2.6.2.2](#).

The following are considered as AESIs:

- Potential severe DILI
A potential severe Drug Induced Liver Injury (DILI) that requires follow-up is defined by the following alterations of hepatic laboratory parameters:
 - o An elevation of AST (aspartate aminotransferase) and/or ALT (alanine aminotransferase) ≥ 3 -fold ULN combined with an elevation of total bilirubin ≥ 2 -fold ULN measured in the same blood sample, or in samples drawn within 30 days of each other, or
 - o Aminotransferase (ALT, and/or AST) elevations ≥ 10 -fold ULN

These lab findings constitute a hepatic injury alert and the subjects showing these lab abnormalities need to be followed up according to the ‘DILI checklist’ provided in the

Proprietary confidential information © 2023 Boehringer Ingelheim International GmbH or one or more of its affiliated companies

ISF. In case of clinical symptoms of hepatic injury (icterus, unexplained encephalopathy, unexplained coagulopathy, right upper quadrant abdominal pain, etc.) without lab results (ALT, AST, total bilirubin) available, the Investigator should make sure that these parameters are analysed, if necessary in an unscheduled blood test. Should the results meet the criteria of hepatic injury alert, the procedures described in the DILI checklist should be followed.

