## **6. GENERAL ANALYSIS DEFINITIONS**

### **6.1 TREATMENT**

For basic study information on the treatment to be administered, cf. **Section 4** of the CTP. Each subject will receive [REDACTED] of BI 1291583 (C-14) as an oral solution containing unlabelled BI 1291583 mixed with [REDACTED] of radiolabelled BI 1291583 (C-14) (2% of total dose).

For statistical analysis of AEs, the following analysis phases are defined for each subject.

Table 6.1: 1 Analysis phases for statistical analysis of AEs, and actual treatment for analysis of laboratory data and vital signs

Study analysis			
phase	Label	Start (inclusive)	End (exclusive)
Screening 	Screening	Date of informed consent	Date/time of administration of study drug
On-treatment	BI 1291583 (C-14)	Date/time of administration of study drug	Date/time of administration of study drug + [REDACTED]  or  12:00 a.m. on day after last contact date (whichever occurs first)
Follow up	F/U	Date/time of administration of study drug + [REDACTED]	12:00 a.m. on day after last contact date

 See [Section 6.7](#) for definition of baseline, which will be used in the statistical analyses of safety laboratory data and vital signs.

AE summary tables will present results for the on-treatment phase only. All AEs will be listed.

Safety laboratory data, vital signs and PK parameters will be analysed with clear differentiation between baseline (cf. [Section 6.7](#)) and on-treatment measurements.

Measurements will be considered on-treatment, if they were taken within the on-treatment phases as defined in [Table 6.1: 1](#).

More details on the technical implementation of these analyses are provided in the ADS Plan of this TSAP.

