### **7.8.3      Vital signs**

The analyses of vital signs (blood pressure and pulse rate) will be descriptive in nature. Descriptive statistics of vital signs over time and for the difference from baseline (see [Section 6.7](#)) will be provided.

Proprietary confidential information © 2023 Boehringer Ingelheim International GmbH or one or more of its affiliated companies.

Clinically relevant findings in vital signs data will be reported as baseline conditions (prior to first administration of study treatment) or as AEs (after first administration of study treatment) if judged clinically relevant by the Investigator, and will be analysed as such.

Unscheduled measurements of vital signs will be assigned to planned time points in the same way as described above for laboratory data. However, for vital signs, descriptive statistics will be calculated by planned post-baseline time point based on the last value of the subject at that planned time point (or assigned to that planned time point). If the time of measurement is missing for a scheduled post-baseline measurement (e.g. for follow-up visits) the scheduled measurement will be used in calculation of descriptive statistics (as time difference between scheduled and unscheduled cannot be assessed). If the time of measurement is missing for an unscheduled post-baseline measurement, this measurement will be listed but will be ignored for the calculation of descriptive statistics.

In descriptive statistic of the Screening visit the planned time points will be used. However, if an unscheduled measurement on the same day as the screening visit exists then the unscheduled assessment will be used in descriptive statistics of Screening visit.

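### The SAP's rule for unscheduled safety values sets no maximum interval and no phase condition, so by-time-point tables can mis-date late values and place some post-dose laboratory values at pre-dose time points.

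*SAP*

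**What the plan says.** SAP 7.8.2 (Laboratory data) gives the assumption: "Unscheduled measurements of laboratory data will be assumed to be repeat measurements of the most recent scheduled measurement". The consequence follows: "unscheduled measurements will be assigned to the planned time point of the previous scheduled measurement". By-time-point statistics are then "based on the worst value of the subject at that planned time point", counting the values assigned there. No maximum interval or phase condition is stated.

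SAP 7.8.3 (Vital signs) carries the assignment over: "Unscheduled measurements of vital signs will be assigned to planned time points in the same way as described above for laboratory data". The value chosen differs: "for vital signs, descriptive statistics will be calculated by planned post-baseline time point based on the last value of the subject". That section makes two exceptions. An unscheduled post-baseline reading without a recorded time is listed but not summarised, and the Screening visit has its own same-day rule.

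Three other provisions bear on this. SAP 6.1 states: "Safety laboratory data, vital signs and PK parameters will be analysed with clear differentiation between baseline" and on-treatment measurements, and it classes a measurement as on-treatment by when it was taken. SAP 6.7 defines baseline in all analyses as the last value before study drug. Protocol Table 5.2.3: 1 fixes the laboratory days: "B: parameters to be determined at Visit 2 on Day -1, Day 2, and Day 15". Profile C (basic haematology only) falls on Days 1, 3, 4, 8 and 10. Profile D is at EoS, which the Flow Chart allows from Day 42 to Day 50.

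**The concern.** The repeat assumption suits a re-draw made soon after a questionable result. It does not suit a schedule with long gaps and symptom-driven sampling. The protocol foresees such sampling. Section 5.2.6.1.4 says that, for symptoms of hepatic injury without liver results, "the Investigator should make sure that these parameters are analysed, if necessary in an unscheduled blood test". Section 6.2.3 requires clinically relevant abnormal values to be monitored until they return to an acceptable level. A subject with an abnormality may therefore have several unscheduled values between two planned draws. The rule reduces them to one worst value at an earlier planned day, and onset and recovery disappear from the summary.

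Time course is much of what a by-time-point safety table conveys after a single dose. The same value can also be on-treatment under SAP 6.1 yet carry a pre-dose time-point label under SAP 7.8.2, and neither section says how the two fit together.

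**Working it through.** The SAP gives no figure for the longest interval, so there is none to reproduce. The gaps follow from the schedule. Inputs: Day 2 = 24 h and Day 15 = 336 h (Flow Chart); EoS = Day 42 to 50 (Flow Chart footnotes); profile days from Table 5.2.3: 1. The Flow Chart is garbled in the available text, so laboratory days are taken from the table. The previous scheduled measurement is read per parameter.

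**Longest gaps**

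| Data | Interval | Calculation | Upper limit of mis-dating |
|---|---|---|---|
| Chemistry, CRP, WBC differential | Day 2 to Day 15 | 336 h - 24 h = 312 h | 13 days |
| Same | Day 15 to EoS | 42 - 15; 50 - 15 | 27 to 35 days |
| Basic haematology | Day 10 to Day 15 (longest between Day 2 and Day 15) | 15 - 10 | 5 days |
| Basic haematology | Day 15 to EoS | as above | 27 to 35 days |

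An unscheduled ALT on Day 12 is thus summarised at Day 2, and one on Day 40 at Day 15. As far as the Flow Chart can be read, vital signs share the Day 2 to Day 15 gap.

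**Crossing dosing (laboratory tables only)**

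- Chemistry: the draws on either side of dosing are at admission on Day -1 (-18 h) and on Day 2 (24 h), 18 + 24 = 42 h apart. An unscheduled sample in the 24 h after dosing has Day -1 as its previous scheduled draw.
- Coagulation: Table 5.2.3: 1 schedules it in profile A only. Any post-dose unscheduled value, on any day, has Screening as its previous scheduled measurement.
- Vital signs: the SAP 7.8.3 statistics under this rule are for post-baseline time points, so this does not arise.

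**Effect on a mean, n = 8**

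The shift is (unscheduled value - scheduled value) / 8. The values below are assumptions for illustration.

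- ALT: all eight subjects at 0.5 x ULN on Day 15, and one with an unscheduled value on Day 40. At 3 x ULN, the reported Day 15 mean is (7 x 0.5 + 3)/8 = 0.81 x ULN. At 10 x ULN it is (7 x 0.5 + 10)/8 = 1.69 x ULN. The Day 15 mean without the late value is 0.50 x ULN.
- Pulse: a later unscheduled 95 bpm replacing 60 bpm at 24 h shifts the mean by (95 - 60)/8 = 4.4 bpm.

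**The case against.** The strongest reply is that the documents contain most of the harm. A reader might infer that a post-dose abnormality would be presented as pre-existing, or that SAP 7.8.2 contradicts SAP 6.1. The documents do not support either inference. SAP 6.7 limits baseline to values before study drug, which protects the baseline value, the reference for change from baseline, and the baseline side of the shift tables. SAP 6.1 and protocol 7.2.5 assign phase by actual time, and SAP 7.8.2 reports clinically significant post-dose abnormalities as adverse events. What remains is an unreconciled label in a laboratory table.

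A reader might also infer that follow-up values will be shown at on-treatment time points. That cannot be checked, because the end of the on-treatment phase is redacted.

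Other safeguards are real. All individual values are listed, out-of-range values are highlighted, and possibly clinically significant values are listed separately. An ALT of 10 x ULN would also be an adverse event of special interest, with its own onset time and table. The worst-value rule at least keeps abnormalities in the summary. Further detail may sit in the company laboratory standard and the ADS plan, which are not available here.

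One could also read the previous scheduled measurement as the previous visit rather than per parameter. That shortens the gaps, but a Day 12 ALT would then go to Day 10, where no ALT is planned.

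These arguments limit the consequence. They do not supply the missing condition: the rule is explicit as written, and no cited SAP section restricts it.

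**Conclusion.** The point holds for by-time-point descriptive tables. Following SAP 7.8.2 as written can mis-date chemistry, CRP and differential values by up to 13 days between Day 2 and Day 15, and by up to 27 to 35 days after Day 15. It can also place a post-dose chemistry value at Day -1 or a post-dose coagulation value at Screening. Basic haematology has shorter gaps before Day 15. Vital signs are affected only at post-baseline time points and subject to the stated exceptions.

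Primary and secondary endpoints, baseline values, individual listings and adverse event reporting are not affected. The conclusion assumes a per-parameter reading and that no unseen company standard adds a limit. The sizes of the mean shifts depend on the assumed values. The change is worth making because a stated rule can give a wrong result in a summary of 8 subjects and correcting it is easy; it is not critical to the trial's conclusions.

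**What to change.** In SAP 7.8.2 and 7.8.3, assign an unscheduled value to the previous scheduled time point only if both conditions hold:

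1. It lies in the same Table 6.1: 1 phase as that measurement, and so never across dosing.
2. It falls within a prespecified short interval of that measurement. The sponsor chooses and states the length; the documents give no basis for a particular figure.

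Leave other unscheduled values out of the by-time-point statistics and list them at their actual day and time. Keep them eligible for the out-of-range, possibly-clinically-significant and last-value-on-treatment outputs. State that the previous scheduled measurement is determined per parameter, and cross-refer to SAP 6.1 and 6.7.

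The cost is a sentence or two in each section and a programming condition. The downside is that some late worst values will no longer appear in the by-time-point summaries, so a reader must look to the listings and flagged outputs for them.
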